2.8 Safety analyses

For all safety analyses, the safety set will be used.

2.8.1 Adverse events (AEs)

In this study, an adverse event is defined as the appearance of (or worsening of any preexisting) undesirable sign(s), symptom(s), or medical condition(s) that occur after a patient's signed Informed Consent has been obtained. With exception of screening failure patients, adverse events that begin or worsen after Informed Consent will be recorded in the Adverse Events eCRF. Summary tables for adverse events have to include only adverse events that started or worsened during the on-treatment period, the treatment-emergent adverse events. Listings will include all reported AEs in the database (except AEs that started after the study completion date) and such AEs that have an onset prior to Study Day 1 are to be flagged in the listing.

Both system organ class (SOC) and preferred term (PT) as listed by the Medical Dictionary for Regulatory Activities (MedDRA, the latest version) will be used for all AE summaries. The following summaries will be produced:

- Overall summary of adverse events
- Adverse events, regardless of study drug relationship, by primary system organ class
- Adverse events, regardless of study drug relationship, by preferred term
- Adverse events, regardless of study drug relationship, by primary system organ class and preferred term
- Adverse events, regardless of study drug relationship, by study period, primary system organ class and preferred term
- Adverse events suspected to be related to study drug, by preferred term
- Adverse events suspected to be related to study drug, by primary system organ class and preferred term
- Serious adverse events, regardless of study drug relationship, by primary system organ class and preferred term
- Adverse events leading to discontinuation, regardless of study drug relationship, by preferred term
- Adverse events leading to discontinuation, regardless of study drug relationship, by primary system organ class and preferred term
- Adverse events leading to dose adjustment or study drug interruption, regardless of study drug relationship, by preferred term
- Adverse events leading to dose adjustment or study drug interruption, regardless of study drug relationship, by primary system organ class and preferred term

Clinical trial safety disclosure

For the legal requirements of ClinicalTrials.gov, the following summaries will be produced:

- On-treatment AEs (i.e., treatment-emergent AEs) which are not serious AEs with an incidence greater than 5% and on on-treatment serious AEs by primary system organ class and preferred term
- Serious AEs suspected to be related to study treatment by primary system organ class and preferred term

If for a same patient, several consecutive AEs (irrespective of study treatment causality, seriousness and severity) occurred with the same system organ class and preferred term:

- a single occurrence will be counted if there is ≤ 1 day gap between the end date of the preceding AE and the start date of the consecutive AE
- more than one occurrence will be counted if there is > 1 day gap between the end date of the preceding AE and the start date of the consecutive AE

For occurrence, the presence of at least one serious AE / serious AE suspected to be related to study treatment / non-serious AE has to be checked in a block e.g., among AE's in a ≤ 1 day gap block, if at least one serious AE is occurring, then one occurrence is calculated for that serious AE.

The number of deaths resulting from serious AEs suspected to be related to study treatment and serious AEs irrespective of study treatment relationship will be provided by primary system organ class and preferred term.

2.8.1.1 Adverse events of special interest / grouping of AEs

The following Adverse Events of special interest (AESIs) will be defined:

- Thrombocytopenia
- Erythropenia (Anemia)
- Leukopenia
- Hemorrhage (all AEs)
- Hemorrhage (Bruising)
- Hemorrhage (GI bleeding)
- Hemorrhage (Intracranial haemorrhage)
- Hemorrhage (Other hemorrhage events)
- Herpes zoster
- Urinary tract infections
- Tuberculosis
- Opportunistic infections
- Pneumonia
- Sepsis and septic shock
- Other infections
- Infections and infestations (SOC)
- Infections and infestations (SOC) without tuberculosis
- Elevated transaminases
- Malignancies
- Progressive multifocal leukoencephalopathy (PML)
- Dizziness
- Weight gain
- Non-melanoma skin cancer (NMSC)
- Hepatitis B reactivation (possible)
- Lipid abnormalites
- Ischemic events
- Hypertension (SMQ)

Selection rules are documented in the 'Compound Case Retrieval Strategy' Sheet (CRS) MedDRA 20.0 version 1.0 (or later version if available at the time point of output generation).

The following summary will be done for each AESI group:

• Overall summary of adverse events of special interest

The following summaries also will be done for each SMQ: Erythropenia, Thrombocytopenia and Leukopenia:

- Time to first newly reported grade 3 or 4
- Duration of newly reported grade 3 or 4

2.8.2 Deaths

On-treatment deaths will be displayed and all deaths will be listed.

2.8.3 Laboratory data

Clinical laboratory tests including hematology, clinical chemistry, urinalysis, lipid panel, coagulation test, and immunology will be done for each patient during the study in accordance with the 'Visit Evaluation Schedule' described in the protocol. If specific safety issue arise, additional, unscheduled laboratory tests/analyses may be done at the discretion of the investigators. A central laboratory will be used for analysis of all specimens collected except for hematology, pregnancy tests, other urine analysis and serology for hepatitis virus and HIV which will be performed locally.

Laboratory data reported will be graded by programming based on the Common Terminology Criteria for Adverse Events (CTCAE) Version 4.0.3, where applicable. A severity grade of 0 will be assigned when the value is within normal limits. (In the case when a laboratory normal range overlaps into the higher (i.e., non-zero) CTC grade, the laboratory value will still be taken as within normal limits and assigned a CTC grade of zero.) Some parameters may be converted in Standard International (SI) units if laboratory measurement with any other unit was reported. For the summarization of laboratory measurements and listing of laboratory measurements, SI unit will be used as default with original or converted measurements. For laboratory tests where grades are not defined by CTCAE, results will be graded by the low/normal/high classifications based on laboratory normal ranges.

The following summary will be produced for laboratory parameters in hematology:

• Shift tables using CTC grades to compare baseline to the worst on-treatment value

All laboratory data will be listed with updated data for the final analysis. Patient with abnormal hematology values will be also listed.

2.8.4 Other safety data

2.8.4.1 ECG and cardiac imaging data

12-lead ECGs including QTcF, QTcB, QT, HR, PR, QRS and RR will be measured for each patient during the study in accordance with the Visit Evaluation Schedule, and will be summarized descriptively. For the calculation of absolute change in cardiac intervals, the average of intervals from the Screening and Baseline recordings will be used as the Baseline for comparison of all post-Baseline intervals.

Table 2-1	Notable electrocardiogram values

Parameters	Parameters Type of abnormality Criterion	
QT, QTcF and QTcB	Change from Baseline New absolute value	Increase > 30 ms to \leq 60 ms Increase > 60 ms > 450 ms to \leq 480 ms > 480 ms to \leq 500 ms > 500 ms
HR	Change from Baseline	Decrease > 25% and resultant HR < 50 bpm Increase > 25% and resultant HR > 100 bpm
PR	Change from Baseline	Increase > 25% and resultant PR > 200 ms Decrease >25% and resultant PR <75 ms
QRS	Change from Baseline	Increase > 25% and resultant QRS > 110 ms Decrease >25 % and resultant QRS < 50 ms

All abnormalities recorded on the e-CRF will be listed by patient. Also, all ECGs will be listed with updated data for the final analysis.

2.8.4.2 Vital signs

Vital signs including systolic blood pressure, diastolic blood pressure, respiratory rate, body temperature, and pulse will be taken in the seated position for each patient during the study.

Criteria for abnormal vital signs is given in Table 2-2.

Table 2-2 Criteria for Clinically Notable Vital Sign Abnormalities

[figure not shown]
	······································	
Parameter	High Threshold	Low Threshold
Systolic Blood Pressure	>160 mm Hg	<85 mm Hg
Diastolic Blood Pressure	>95 mm Hg	<50 mm Hg
Respiratory rate	>24 per minute	<8 per minute
Temperature	≥37.5°C	≤35.0°C
Sitting pulse	≥120 bpm	≤50 bpm

All vital signs will be listed with updated data for the final analysis.

2.11 Patient-reported outcomes

Outputs of all EORTC QLQ-C30 and summary of Seven-day modified MFSAF questionnaires were reported in "the Week 24 CSR" and not applicable in this document. The Change in total symptom score by Seven-day modified MF-SAF v2.0 questionnaire will be summarized and listed with updated data for the final analysis.

2.14 Interim analysis

A single interim analysis was conducted by the Novartis statistician.

With regard to detailed plan for the interim analysis, please refer to Section 4.9 in "CINC424A2202 RAP Module 3 Detailed statistical methodology Amendment 2".

3 Sample size calculation

The planned sample size of 110 was determined based on the single-sample binomial test (normal approximation).

Study INCB 18424-351 is a randomized, double-blind, placebo-controlled study comparing the efficacy and safety of INC424 to a matched placebo in patients with PMF or post-PV/ET MF. In this study, the same primary efficacy variable, i.e., proportion of patients achieving \geq 35% reduction in spleen volume from Baseline at Week 24 as measured by MRI (or CT scan), is evaluated. The result of Study INCB 18424-351 provided a response rate of 41.9% in INC424 group while a response rate of 0.7% was observed in the placebo group.

Based on the results obtained in Study INCB 18424-351, the proportion of patients on this study achieving \geq 35% reduction in spleen volume from Baseline at Week 24 as measured by MRI (or CT scan) is expected to be 0.35. From the aspect of clinical benefit in patients with PMF or post-PV/ET MF, a threshold of 0.2 was set for the null hypothesis.

An interim analysis is planned in this study. If the study had no interim analysis (1-stage approach), the required sample size of 110 provides power of 0.951 with one-sided type I error rate of 0.025 under response rate of 0.2 and 0.35 for null and alternative hypotheses. The power for the group sequential (i.e., 2-stage) design accruing 110 total patients with the same final time-point boundary ($\geq 31/110$) and an interim analysis conducted after 50 patients using an O'Brien-Fleming type interim analysis boundary ($\geq 19/50$) is approximately 0.95. Therefore, the effect of the interim analysis on the overall study power is negligible.

4 Change to protocol specified analyses

Not applicable.

5 Appendix

5.1 Imputation rules

5.1.1 Study drug

Not applicable.

5.1.2 AE date imputation

Concomitant medication (CMD) imputation rules in Section 5.1.3 will be applied for AE date imputation.

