5.1.3 Concomitant medication date imputation

The following Table 5-1 explains the notation used in the logic matrix. Please note that, if the date is completely missing, it will not be imputed.

Table 5-1 CMD/ treatment date abbreviations

	Day	Month	Year
Partial CMD Start Date	Not used	MON	YYYY
Treatment Start Date (TRTSTD)	Not used	TRTM	TRTY

The following matrix Table 5-2 describes the possible combinations and their associated imputations. In the boxes the upper text indicates the imputation and the lower text indicates the relationship of the CMD start date to the treatment start date (TRTSTD).

Table 5-2CMD partial date imputation algorithm

	MON MISSING	MON < TRTM	MON = TRTM	MON > TRTM
YYYY MISSING	(C)	(C)	(C)	(C)
	Uncertain	Uncertain	Uncertain	Uncertain
YYYY < TRTY	(D)	(A)	(A)	(A)
	Before TRTSTD	Before TRTSTD	Before TRTSTD	Before TRTSTD
YYYY = TRTY	(C)	(A)	(C)	(B)
	Uncertain	Before TRTSTD	Uncertain	After TRTSTD
YYYY > TRTY	(E)	(B)	(B)	(B)
	After TRTSTD	After TRTSTD	After TRTSTD	After TRTSTD

The following Table 5-3 is the legend to the above table.

Table 5-3	CMD/treatment date relationship and imputation legend
-----------	---

Relationship	
Before TRTSTD	Partial date indicates CMD start date prior to Treatment Start Date
After TRTSTD	Partial date indicates CMD start date after Treatment Start Date
Uncertain	Partial date insufficient to determine relationship of CMD start date to Treatment Start Date
Imputation calculation	
(A)	15MONYYYY
(B)	MAX(01MONYYYY, TRTSTD+1)
(C)	TRTSTD+1
(D)	01JULYYYY
(E)	01JANYYYY

5.1.3.1 **Prior therapies date imputation**

CMD imputation rules in Section 5.1.3 will be applied for prior therapies imputation with exception that for scenario (B) will be replaced to be 'Treatment Start Date (TRTSTD) - 1'.

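### SAP 5.1.2 imputes partial AE start dates without looking at the AE end date, so an AE that ended before the first dose can be dated Study Day 2 and counted as treatment-emergent

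*SAP*

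**What the plan says.** SAP 5.1.2 has no AE-specific algorithm. It states that the medication rules of 5.1.3 "will be applied for AE date imputation".

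Tables 5-1 to 5-3 in SAP 5.1.3 use four quantities: month and year of the partial start date, and month and year of TRTSTD. Three kinds of partial date are labelled Uncertain, defined as "Partial date insufficient to determine relationship of CMD start date to Treatment Start Date": same year and month as first dose, same year with month missing, and year missing. All take rule (C), TRTSTD+1. The text before the matrix adds that "if the date is completely missing, it will not be imputed".

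SAP 5.1.3.1 reuses the rules for "prior therapies imputation with exception that for scenario (B) will be replaced to be 'Treatment Start Date (TRTSTD) - 1". Only (B) is changed. SAP 5.1.3.3, on other imputations, is marked not applicable.

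SAP 2.8.1 sets the use of the dates: "Summary tables for adverse events have to include only adverse events that started or worsened during the on-treatment period, the treatment-emergent adverse events". AEs are recorded from informed consent, and those with onset before Study Day 1 are flagged in the listings. SAP 2.1.1 starts the on-treatment period on the day of first dose and numbers that day 1. Protocol 8.1.1 collects AE end dates as well as start dates.

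**The concern.** Placing an AE of uncertain order after the first dose is a common cautious convention. It is not cautious when a recorded end date shows that the AE was over before treatment began. The rule then produces an impossible record and attributes a pre-treatment event to the treatment period.

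The affected outputs are still planned in this SAP: the AE summaries in 2.8.1, including the one by study period; the pre-treatment flag in the listings; and time to first, and duration of, newly reported grade 3 or 4 events for erythropenia, thrombocytopenia and leukopenia in 2.8.1.1. The disclosure counts in 2.8.1 also compare the end date of one AE with the start date of the next, so a start later than its own end can disturb them.

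Two related rules share the weakness. A therapy recorded as prior can be dated after the first dose. And the text and Table 5-2 disagree on dates with neither month nor year.

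**Working it through.** The plan states no figure on this point, so the check is to run Tables 5-2 and 5-3 on worked cases.

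**Inputs.** Rules (A) to (E) and the matrix: SAP 5.1.3. Exception for prior therapies: 5.1.3.1. Study day: SAP 2.1.1, date − TRTSTD + 1 on or after first dose, date − TRTSTD before it. Illustrative first dose: 20 March 2012.

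| Record | Rule | Imputed start | Study day |
|---|---|---|---|
| AE, start March 2012 (day unknown), ended 10 March 2012 | (C) | 21 March 2012 | 2 |
| AE, start 2012 (day and month unknown), ended 10 March 2012 | (C) | 21 March 2012 | 2 |
| AE, start February 2012 (day unknown) | (A) | 15 February 2012 | −34 |
| Prior therapy, March 2012 or 2012 only | (C) | 21 March 2012 | 2 |
| Prior therapy, April 2012 | (B), with exception | 19 March 2012 | −1 |
| Prior therapy, 2008 only | (D) | 1 July 2008 | before first dose |

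**AEs.** In the first two rows the AE ended on Study Day 10 − 20 = −10, yet its imputed start is 21 − 20 + 1 = 2. Taking duration as end − start + 1 (my assumption; the SAP gives no AE duration formula), the result is 10 − 21 + 1 = −10 days. Study Day 2 lies in the on-treatment period, so the AE is tabulated as treatment-emergent and is not flagged. Inclusion also covers AEs that worsened on treatment, but one that ended before the first dose cannot have done so. Its imputed start is what brings it in.

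**Prior therapies.** A therapy whose partial date points after first dose (B) is moved to the day before it. One whose date is merely uncertain (C) stays on the day after it. Two records both collected as prior are thus treated inconsistently.

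**Completely missing dates.** The text leaves them unimputed. The Table 5-2 cell for missing year and missing month assigns (C), Study Day 2. Both cannot apply.

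**How often rule (C) is reached.** Protocol 5.1 limits Screening plus Baseline to 42 days. For a 30-day month and a uniformly placed first dose, the mean number of earlier days in the same month is (0 + 1 + … + 29)/30 = 14.5, and 14.5/42 = 34.5%. Enumeration over two calendar years, with onset uniform over the window, gives for AEs with only the day missing:

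- 42-day window: 35%
- 28-day window: 52%
- 7-day window: 87%

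With day and month both missing the share is 94% to 99%. These are shares of pre-dose onsets sent to (C), given a partial date.

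**The case against.** The strongest reply is that very few records will be affected. AE dates are sought at every visit (Protocol 8.1.1), entries pass automatic checks (9.3), and missing values are queried (9.4). Eligibility requires platelets of at least 100,000/µL and ANC of at least 1,000/µL (5.2), so severe pre-dose platelet or neutrophil events should be rare. All this stands. Anemia is the main exception, because hemoglobin below 10 g/dL is a qualifying risk factor and an abnormality needing transfusion counts as an AE.

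It is also fair that TRTSTD+1 is a reasonable choice where no end date settles the order, and that rules (A) and (D) respect a partial start date that itself shows pre-treatment onset. The point is confined to (C) combined with an earlier recorded end date.

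On completely missing dates, one can read the sentence as governing and the table cell as redundant. That is plausible, but nothing says so, and the SAP does not state how an AE with no start date is classified. A reader might infer that such AEs drop out of every treatment-emergent table; the documents do not settle this.

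A reader might also infer that all undated prior therapies land after first dose. They do not: the text exempts completely missing dates, and therapies with an earlier year or month go to (A) or (D). Nor do the documents show that a prior MF drug dated Study Day 2 becomes deviation M04 in Table 5-4 with loss of later data. Nothing says that deviations are derived from imputed dates.

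**Conclusion.** The AE rule is defective as written. For a partial start date in the Uncertain cells and a recorded end before the first dose, it gives a start after the end and a false treatment-emergent classification, in tables that this SAP still produces. That follows from the stated rules and needs no assumption.

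The size cannot be fixed from the documents, because the number of partial dates is not given; it is probably small. A reader might take the 35% as a misclassification rate. It is not. It assumes uniform onset over the full 42 days and counts every day-missing pre-dose onset that reaches (C). Only those with an end date before first dose are provably wrong, and that share is unknown.

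The prior-therapy inconsistency is real but has little effect here, since SAP 2.4.2 says the therapy summaries were reported in the Week 24 CSR. The conflict over completely missing dates is a drafting matter, but it should be settled before programming.

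**What to change.** In SAP 5.1.2, add that an imputed AE start may never be later than the recorded end date, and that an AE whose end date precedes TRTSTD is classed as pre-treatment. Keep TRTSTD+1 for AEs whose order is truly uncertain. In the example, the AE that ended on 10 March 2012 would start no later than Study Day −10 and be flagged. An AE that ended on the day of first dose would be capped at Study Day 1 and remain treatment-emergent.

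In 5.1.3.1, extend the TRTSTD−1 cap to scenario (C).

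In 5.1.3, reconcile the sentence on completely missing dates with the Table 5-2 cell, and state whether an undated AE counts as treatment-emergent. Simply deleting the sentence is not free of cost: it would create artificial Study Day 2 onsets, which would enter the time-to-first grade 3/4 summaries. One option is to count such AEs as treatment-emergent without giving them a date.

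The cost is a few sentences and a change to the date-imputation program. If the Week 24 CSR used the same rules, which these documents do not show, note the change there so that the two sets of AE tables can be compared.

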5.1.3 Concomitant medication date imputation

The following Table 5-1 explains the notation used in the logic matrix. Please note that, if the date is completely missing, it will not be imputed.

Table 5-1 CMD/ treatment date abbreviations

	Day	Month	Year
Partial CMD Start Date	Not used	MON	YYYY
Treatment Start Date (TRTSTD)	Not used	TRTM	TRTY

The following matrix Table 5-2 describes the possible combinations and their associated imputations. In the boxes the upper text indicates the imputation and the lower text indicates the relationship of the CMD start date to the treatment start date (TRTSTD).

Table 5-2CMD partial date imputation algorithm

	MON MISSING	MON < TRTM	MON = TRTM	MON > TRTM
YYYY MISSING	(C)	(C)	(C)	(C)
	Uncertain	Uncertain	Uncertain	Uncertain
YYYY < TRTY	(D)	(A)	(A)	(A)
	Before TRTSTD	Before TRTSTD	Before TRTSTD	Before TRTSTD
YYYY = TRTY	(C)	(A)	(C)	(B)
	Uncertain	Before TRTSTD	Uncertain	After TRTSTD
YYYY > TRTY	(E)	(B)	(B)	(B)
	After TRTSTD	After TRTSTD	After TRTSTD	After TRTSTD

The following Table 5-3 is the legend to the above table.

Table 5-3	CMD/treatment date relationship and imputation legend
-----------	---

Relationship	
Before TRTSTD	Partial date indicates CMD start date prior to Treatment Start Date
After TRTSTD	Partial date indicates CMD start date after Treatment Start Date
Uncertain	Partial date insufficient to determine relationship of CMD start date to Treatment Start Date
Imputation calculation	
(A)	15MONYYYY
(B)	MAX(01MONYYYY, TRTSTD+1)
(C)	TRTSTD+1
(D)	01JULYYYY
(E)	01JANYYYY

5.1.3.1 **Prior therapies date imputation**

CMD imputation rules in Section 5.1.3 will be applied for prior therapies imputation with exception that for scenario (B) will be replaced to be 'Treatment Start Date (TRTSTD) - 1'.

5.1.3.2 Post therapies date imputation

CMD imputation rules in Section 5.1.3 will be applied for post therapies imputation.

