2.1.1 General definitions

Study drug and study treatment

Both study drug and study treatment refer to INC424.

Date of first administration of study drug

The date of first administration of study drug is defined as the first date when a nonzero dose of study drug is administered and recorded on the dose administration record (DAR) page of the electronic case report form (eCRF).

Date of last administration of study drug

The date of last administration of study drug is defined as the last date when a nonzero dose of study drug is administered and recorded on DAR page of the eCRF.

Study day

Study day 1 is the date of first administration of study drug.

The study day for all assessments will be calculated as follows:

1. If date of assessment occurred on or after the start of study treatment, then

Study day = Date of assessment - Start date of study treatment + 1.

2. If date of assessment occurred before the start of study treatment, then

Study day = Date of assessment - Start date of study treatment.

The study day will be displayed in the data listings.

Baseline

Unless otherwise specified, the baseline measurement for any parameter is defined as the last non-missing pre-dose value (scheduled or unscheduled) before the first administration of study drug.

On-treatment assessment/event

On-treatment period is from day of first dose of study drug to 30 days after last dose of INC424.

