2.7 Analysis of secondary efficacy objective(s)

Most secondary analyses were reported in "the Week 24 CSR" and not applicable in this document. The below analyses which were previously performed will be repeated with updated data for the final analysis.

Best response rate

The best response rate is defined as the proportion of patients achieving $\geq 35\%$ reduction in spleen volume from Baseline at any post-baseline assessment. The best response rate will be estimated with an associated 95% confidence interval based on the normal approximation.

Duration of maintenance of a greater or equal to 35% reduction from Baseline in spleen volume

For patients who had at least one $\geq 35\%$ reduction in spleen volume from Baseline at postbaseline, the duration of response will be calculated. The start date of the duration is defined as the first spleen volume measurement that is $\geq 35\%$ reduction from Baseline, and the end date of the response duration is defined as the earliest of the following:

- Death.
- $A \ge 25\%$ increase in spleen volume by MRI compared to Baseline.
- Splenic irradiation.

- Leukemic transformation as defined by a bone marrow or a peripheral blood blast count of $\geq 20\%$.
- Splenectomy.

In the event that a patient experiences leukemic transformation, requires therapy with splenic irradiation, or experiences a $\geq 25\%$ increase in spleen volume by MRI compared to Baseline, the study drug must be permanently discontinued. Therefore, the end date of the duration will be defined as the earliest date for one of the following for patient with any event of disease progression:

- Date of death.
- Assessment date of spleen volume with a \geq 25% increase compared to Baseline measured by MRI.
- Date of leukemic transformation captured on the e-CRF page "Leukemic transformation".
- Date of Splenic irradiation/Splenectomy captured on either the "Concomitant medications/Significant non-drug therapies" or "Antineoplastic therapies since discontinuation of study drug" e-CRF pages.

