If a patient undergoes splenectomy, and the investigator believes that it is in the patient's best interest to continue treatment with INC424 due to symptomatic improvement, the patient may continue treatment assuming she/he has fully recovered from the splenectomy procedure within 12 weeks. Even if she/he continues therapy with INC424, the event will be assumed to have occurred for that patient. Note that the date of splenectomy will be recorded on the e - CRF page "Concomitant medications/Significant non-drug therapies" if that patient continues treatment with INC424.

The censoring date is defined as the date of the last adequate assessment of spleen volume for patients with no event of disease progression. Patients who had more than 1 consecutive missing spleen volume assessment will be censored at the last adequate assessment prior to the consecutive missing assessments, regardless of the occurrence of a subsequent death or any event of disease progression.

The duration of response will be evaluated using a Kaplan-Meier estimate. Note that the analysis will be performed only for patients who achieved a least one \geq 35% reduction in spleen volume at any time on study.

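### SAP 5.1.3.2 imputes partial post-therapy dates from treatment start, so a month-missing date can fall before last dose and, if SAP 2.7 uses it, before the response it should end

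*SAP*

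**What the plan says.** SAP 5.1.3 gives a matrix for partial start dates of concomitant medication. It compares the reported month and year with those of treatment start (TRTSTD) and assigns one of five rules. Two matter here:

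- Rule C gives TRTSTD+1. It applies when the order is unclear ("Partial date insufficient to determine relationship of CMD start date to Treatment Start Date"), which includes a missing month in the treatment-start year.
- Rule E gives 1 January of the reported year. It applies to a missing month in a later year.

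The matrix stops short of fully missing dates: "if the date is completely missing, it will not be imputed".

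For prior therapies, SAP 5.1.3.1 adapts the matrix, "with exception that for scenario (B) will be replaced to be" the day before treatment start. For post therapies, SAP 5.1.3.2 adapts nothing: the rules "will be applied for post therapies imputation". A usable reference date is already defined in SAP 2.1.1: "The date of last administration of study drug is defined as the last date when a nonzero dose of study drug is administered".

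SAP 2.7 defines the duration of response, whose analysis is repeated for the final report. For patients with a progression event, "the end date of the duration will be defined as the earliest date for one of the following", a list that includes splenic irradiation and splenectomy. One of the two source pages for these is "Antineoplastic therapies since discontinuation of study drug".

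**The concern.** A therapy recorded as given after discontinuation should not be dated Study Day 2. The matrix does this because it only asks whether a therapy began before or after treatment start. For a post therapy the relevant boundary is the end of treatment, and the matrix does not use it.

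The visible use of that page in this SAP is the end date of response. If an imputed date enters there, a responder with a real splenectomy or irradiation could have a response that ends before it starts. The analysis includes responders only, so a single wrong date carries some weight in the Kaplan-Meier estimate. No rule is given for a negative duration, so the decision would fall after database lock.

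**Working it through.** No figure in the plan needs reproducing. The check applies SAP Tables 5-2 and 5-3 to month-missing dates. Durations are simple date differences. All calendar dates are illustrative, because the documents contain no patient dates.

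**Inputs**
- SAP 2.1.1: treatment start is Study Day 1, so TRTSTD+1 is Study Day 2.
- SAP 2.7: response starts at the first spleen volume with a reduction of at least 35%.
- Protocol 7.2.1.1 and Table 7-1: MRI at Weeks 12, 24, 36 and 48. Week 12 is Day 84, with a window of 7 days either way, so the earliest on-schedule response is Day 77.

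**Rule C (month missing, year of first dose)**
- Day 77 − Day 2 = 75 days; Day 84 − Day 2 = 82 days.
- The imputed end therefore precedes every on-schedule response, whatever the calendar dates.
- Example: first dose 15 Mar 2012, Day 84 response 6 Jun 2012, last dose 10 Nov 2012, splenectomy recorded as 2012 on the post-discontinuation page. Rule C gives 16 Mar 2012, a duration of −82 days.
- With a floor at last dose + 1: max(1 Jan 2012, 11 Nov 2012) = 11 Nov 2012, a duration of +158 days.
- Latest compatible date: 31 Dec 2012, a duration of 208 days.

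**Rule E (month missing, later year)**
- The order is reversed when the response falls after 1 January of the event year.
- Reversed: first dose 20 Oct 2011, response 11 Jan 2012, true event 15 Aug 2012 (+217 days). The imputed date is 1 Jan 2012, a duration of −10 days. With a Week 24 response (4 Apr 2012) it is −94 days.
- Shortened only: same first dose and 11 Jan 2012 response, last dose 2 Mar 2013, true event 15 Aug 2013 (582 days). The imputed date is 1 Jan 2013, giving 356 days, and it still precedes last dose.
- For an event in the calendar year after first dose, number the start days 1 to 365, so that 1 January is day 366. Reversal for a Day 84 response needs d + 83 > 366, so d ≥ 284 (11 Oct): 82 of 365 start dates. For a Day 168 response, d + 167 > 366, so d ≥ 200 (19 Jul): 166 of 365. These fractions assume uniform start dates and on-schedule scans, and are conditional on such a record existing. They are not incidences.

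**Interaction with censoring**
- SAP 2.7 censors at the last adequate scan before more than one consecutive missing assessment.
- In the rule C example, only the Day 252 scan (21 Nov 2012) falls between last dose and 31 Dec 2012, so the event stands.
- Suppose instead the record says 2013. The floored date is max(1 Jan 2013, 11 Nov 2012) = 1 Jan 2013, an event at 209 days. At the latest compatible date, 31 Dec 2013, the Day 336 scan (13 Feb 2013) has also been missed. The patient is then censored at the Day 168 scan (29 Aug 2012), at 84 days. This assumes that scans falling due after discontinuation count as missing, which SAP 2.7 does not state.

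**The case against.** The strongest reply is that the harm needs a link the SAP does not make. SAP 2.7 takes dates from named eCRF pages and never cites the imputation section. SAP 5.1.3.3, which marks other imputations as not applicable, can be read to mean that efficacy event dates are not imputed at all. The Week 24 analysis plan (RAP Module 3 Amendment 2) is not among the documents and may contain a rule. A reader might infer that the planned duration of response is wrong as it stands. The documents do not support that, and every statement above about duration is conditional on the imputed date being used. What stands without the link is that 5.1.3.2 yields a date that contradicts the record, and that 2.7 is silent on partial dates.

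A reader might also use the Follow-up Visit to put a firm upper limit on the date error. The documents do not allow it. Protocol 4.1 counts 30 (+10) days from last dose, but Protocol 7.1.5 also allows counting from the End of Treatment Visit, as Table 7-2 does, and 7.1.4 asks only that this visit occur as soon as possible. Protocol 6.2.4.2 keeps patients who stop for an adverse event under longer follow-up.

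The floor is not perfect either. Protocol 6.3.4 allows a taper of 1 to 2 weeks, so a new therapy could begin shortly before the last dose. Flooring could also move an event ahead of two missed scans and so count it when it should be censored. The cap and the sensitivity run in the proposed change address these cases in part.

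Finally, the number affected is probably small. It takes a responder, a splenectomy or irradiation, a missing month, and a query under Protocol 9.4 that was never resolved. No count is given.

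**Conclusion.** The point holds as a minor one. SAP 5.1.3.2 states a rule that gives an impossible date for its own class of record: Study Day 2 for a month-missing therapy in the first-dose year, and possibly a date before last dose in a later year. If SAP 2.7 uses that date, rule C always makes the duration negative for an on-schedule responder, by at least 75 days. Rule E can make it negative or only too short.

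This rests on two inferences: that post therapies means the post-discontinuation page, and that imputed dates reach SAP 2.7. The date error moves the end of response earlier, so it does not favour the drug. The primary endpoint does not use these dates.

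A similar concern might be inferred for on-treatment splenectomy, where "Even if she/he continues therapy with INC424, the event will be assumed to have occurred for that patient" and the date comes from the concomitant and non-drug page. Last dose is no floor for such a record, and the documents do not point to one replacement rule, so the point is confined to the post-discontinuation page.

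**What to change.** In SAP 5.1.3.2, for records on the post-discontinuation page with a reported year, impute max(earliest date compatible with the partial date, date of last administration + 1), capped at the latest date compatible with the partial date. The cap keeps the imputed date inside what the site reported, even when that interval ends before last dose.

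In SAP 2.7, state that this date is used for the duration of response and that censoring after more than one consecutive missing assessment still applies. Add one sensitivity run with these dates set to the latest compatible date. That run also shows any patient for whom the censoring rule would change the result.

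The cost is a few sentences, minor programming and one extra run. No new data are needed, because last dose and scan dates are already collected.
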